8.7.1.2 VISIT 5 (OIT Visit 2)

Visit 5 will be conducted 4-6 weeks after randomisation (visit 4) and will take up to 8 hours. Note that there must be at least 4 weeks between each OIT visit (visits 4, 5, and 6).

- 1. Confirm continuation of participation.
- 2. Physical Examination, current medical history & vital signs to be assessed prior to OIT schedule: Weight, length, EASI Score & history of wheeze. The following will be confirmed to be normal and a statement to this effect recorded in the medical notes: general physical examination with

chest auscultation, Peripheral arterial pulse, heart rate, systolic and diastolic blood pressure, respiratory rate, and oxygen saturation.

- 3. Unplanned visits: Any unplanned visits since the last visit and the reason for the visit, will be captured.
- 4. Collect diary from previous visit: Collect completed diary pages from previous visit and review. Any AEs will be recorded in the participant's medical notes and on the AE Log.
- 5. OIT dose escalation schedule: will be conducted as per the trial OIT SOPs. The participant will escalate to higher doses than the previous visit. Results of the OIT must be recorded in the **participant's medical notes**.
- 9. Prescribe allocated study product for home: Complete study prescription for the pharmacy/unblinded team to dispense an adequate amount of the allocated study product. An adequate number of tins should be prescribed to supply the participant with enough formula to last until the next visit (or until further product is received at home if no further OIT visits are required). Pharmacy/unblinded team will complete appropriate accountability logs and, if necessary, the Sharp product request form to request further product for home delivery using the appropriate request form.
- 6. Providing diary and instructions for use: Give participants diary and instructions for filling in.
- 7. Record AEs: Any AEs occurring from this visit must be recorded in the participant's medical notes and on the AE Log (see section 10).

The participants will be advised to continue dosing at home after this visit, with doses slightly lower to the one they managed to tolerate at this visit, as per the trial OIT SOPs.

8.7.1.3 VISIT 6 (OIT Visit 3)

Visit 6 will be conducted 8-12 weeks after randomisation and will take up to 8 hours. Note that there must be at least 4 weeks between each OIT visit (visits 4, 5, and 6).

- 1. Confirm continuation of participation.
- Physical Examination, current medical history & vital signs to be assessed prior to OIT schedule: Weight, length, EASI Score & history of wheeze. The following will be confirmed to be normal and a statement to this effect recorded in the medical notes: general physical examination with chest auscultation, Peripheral arterial pulse, heart rate, systolic and diastolic blood pressure, respiratory rate, and oxygen saturation.
- 3. Unplanned visits: Any unplanned visits since the last visit and the reason for the visit, will be captured.

- 4. Collect diary from previous visit: Collect completed diary pages from previous visit and review. Any new AEs will be recorded in the participant's medical notes and on the AE Log and any previous AEs will be followed-up and marked as resolved if appropriate.
- 5. OIT dose escalation schedule: will be conducted as per the trial OIT SOPs. The participant will escalate to higher doses than the previous visit. Results of the OIT must be recorded in the **participant's medical notes**.
- 6. Prescribe adequate amount of allocated study product for home: Complete study prescription for the pharmacy/unblinded team to dispense the allocated study product to *randomised participants*. An adequate number of tins should be prescribed to supply the participant with enough formula to last until further product is received at home. Pharmacy/unblinded team will also complete appropriate accountability logs and the Sharp product request form to request further product for home delivery using the appropriate request form.
- 7. Provide diary and instructions for use: Give participants diary and instructions for filling in.
- 8. Record AEs: Any AEs occurring from this visit must be recorded in the participant's medical notes and on the AE Log (see section 10).
- 9. Provide stool sample containers for the next visit: Provide parents with containers for the collection of stool samples at home. Parents should take samples as close to visit 7 as possible, and only from participants whose parents have provided **consent** for these additional samplings.

The participants will be advised to continue dosing at home after this visit, with doses close to the one they managed to tolerate, or feed freely, as per the trial OIT SOPs.

8.7.2 Telephone Calls

There will be two telephone calls as below:

- **Telephone call 1:** Telephone call 1 is for participants who do not undergo OIT. It will take place 12 weeks (+/- 2w) after randomisation. There will be no telephone call 1 for participants undergoing OIT as these participants will remain engaged with the researchers through the OIT visits.
- **Telephone call 2:** Telephone call 2 will take place for all participants 36 weeks (+/- 2w) after randomisation.

The following will take place for telephone call 1 and 2:

- 1. Parents will be asked if they have any questions;
- 2. They will be asked to confirm they are happy to continue with the trial;
- 3. They will be asked if there was any problem with provision of the trial formula;
- 4. They will be asked if they have been using the trial formula as advised;
- 5. They will be reminded of the trial formula expiration and advised to discard any formula that has expired or exceeded the shelf life.

- 6. They will be asked if their child has had any allergic episode where they needed to use an EpiPen, or any other adverse events;
- 7. They will be asked whether they have attended any unplanned visits and why;
- 8. They will be reminded to fill in the diary and asked if they have enough copies of the diary;
- 9. They will be reminded of the date of their next visit;
- 10. They will be asked whether their child has been introduced to any new foods.

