7 PARTICIPANT TIMELINE, ASSESSMENTS AND PROCEDURES

	V ₁	V ₂	V ₃	V_4	V 5	V ₆	TC1	V ₇	TC2	V ₈	V۹
	Screening visit	phf challenge	CM challenge ¹	1 st OIT Visit ²	2 nd OIT Visit ²	3 rd OIT Visit ²	Telephone call 1 ¹	Mid-study assessment	Telephone call 2 ³	1 st part DBPCFC to CM	2 nd part DBPCFC to CM
ACTIVITY		3-21 Ds from V1	2-28 Ds from V2	2-6 Ws from V2	4-6 Ws from Randomisation (V4) ⁴	8-12 Ws from Randomisation (V4) ⁴	12 Ws (+/- 2) from Randomisation (V3)	24 Ws (+/- 2) from Randomisation (V3 or V4)	36 Ws (+/- 2) from Randomisation (V3 or V4)	48 Ws (+/- 2) from Randomisation (V3 or V4)	1-4 Ws from V8
Informed consent signed	X										
Assessment of eligibility	х	х	x								
Confirmation of eligibility			x	х							
Demographics & review of medical history and diet ⁵	X										x
Assessment of Adverse events				Х	x	х	х	х	х	х	х
Physical Examination, current medical history & vital signs ⁶	X	x	x	X	х	X		х		x	x
Skin Prick Testing ⁷	Х									х	
Blood samples for antigen specific IgE ⁸	X									x	
Blood samples for safety markers ⁹	X										
Blood samples for storing ¹⁰	X							х		х	
Buccal samples for storing ¹¹		х						х		х	
Provide stool sample containers		x	(x)			Х		х			
Collection of stool samples for storing ¹²			х	Х				х		х	
Randomisation ¹³			(x)	х							
Dispensing of randomised			(x)	Х	х	х					
study product for home ¹⁴ Provide diary and instructions								v		v	
			(x)	X	X	X		X		X	
Collect and review Diary					X	X		X		X	X
Oral Immunotherapy (OIT)				X	X	X					
Oral Challenge and follow-up call		X	X							X	X
Telephone questions ¹⁵							х		х		

¹ Only applicable to participants with a negative reaction to pHF at V2.

² Only applicable to participants with a positive reaction to pHF V2.

³Telephone call 2 will take place for all participants 36 weeks (+/- 2w) after randomisation.

⁴ There must be at least 4 weeks between each of the OIT visits (V4, V5 and V6).

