8.7.1.1 VISIT 4 (OIT Visit 1)

Visit 4 will be conducted 2-6 weeks after visit 2 (these participants skipped visit 3) and will take up to 8 hours.

Participants will undergo the following assessments:

- 1. Confirm eligibility to continue participation.
- 2. Allocation to randomised treatment: Participants attending visit 4 (these are the participants with a positive result to VISIT 2 (Open Challenge to pHF) will be randomised (see section 8.5).
- 3. Collect stool samples: These will be collected only where **consent** has been provided and stored locally until transferred to the central laboratory.
- 4. Physical Examination, current medical history & vital signs to be assessed prior to OIT schedule: Weight, length, EASI Score & history of wheeze. The following will be confirmed to be normal and a statement to this effect recorded in the medical notes: General physical examination with chest auscultation, Peripheral arterial pulse, heart rate, systolic and diastolic blood pressure, respiratory rate, and oxygen saturation.
- 5. OIT dose escalation schedule: will be conducted as per the trial OIT SOPs. Results of the OIT must be recorded in the **participant's medical notes**.
- 6. Prescribe allocated study product for home: Complete study prescription for the pharmacy/unblinded team to dispense an adequate amount of the allocated study product. An adequate number of tins should be prescribed to supply the participant with enough formula to last until the next visit (or until further product is received at home if no further OIT visits are required). Pharmacy/unblinded team will complete appropriate accountability logs and, if necessary, the Sharp product request form to request further product for home delivery using the appropriate request form.
- 7. Provide diary and instructions for use: Give participants diary and instructions for filling in.
- 8. Record AEs: Any AEs occurring from this visit must be recorded in the participant's medical notes and on the AE Log (see section 10).

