8.7.3 Mid-Trial Visit 8.7.3.1 VISIT 7 (Mid Trial Visit)

Visit 7 will be conducted 24 weeks (+/- 2 weeks) from randomisation and will last up to two hours. Adherence to treatment will be checked by the research team by reviewing the diary. AEs will be reviewed and recorded **in the participant's medical notes**.

- 1. Continuation of participation will be reconfirmed.
- 2. Physical Examination, current medical history & vital signs: Weight, length, EASI Score & history of wheeze. The following will be confirmed to be normal and a statement to this effect recorded in the medical notes: general physical examination with chest auscultation, Peripheral arterial pulse, heart rate, systolic and diastolic blood pressure, respiratory rate, and oxygen saturation.
- 3. Collection of Buccal samples, blood samples and stool samples for storing: These will be collected only where **consent** has been provided, and stored locally until transferred to the central laboratory.
- 4. Unplanned visits: Any unplanned visits since the last visit and the reason for the visit, will be captured.
- 5. Collect diary from previous visit: Collect completed pages from previous visit and review. Any new AEs will be recorded in the participant's medical notes and on the AE Log and any previous AEs will be followed-up and marked as resolved if appropriate.
- 6. Provide diary and instructions for use: Give participants diary and instructions for filling in.
- 7. Provide stool sample containers for the next visit: Provide parents with containers for the collection of stool samples at home. Parents should take samples as close to visit 8 at possible, prior to the start of the challenge, and only from participants whose parents have provided **consent** for these additional samplings.
- 8. Record AEs: Any AEs occurring from this visit must be recorded in the participant's medical notes and on the AE Log (see section 10).
- 9. Record any new foods: Any new foods that have been introduced since the start of the study must be recorded in the participant's medical notes and appropriate CRF.

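### Infants who finish oral immunotherapy after visit 4 or 5 get no telephone call 1, so a pHF-reactive infant still on trial formula can go up to 26 weeks without a scheduled contact or adverse event assessment

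*Protocol*

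**What the plan says.** Protocol section 8.7.2 sets two telephone calls. On the first it says: "Telephone call 1 is for participants who do not undergo OIT", and "It will take place 12 weeks (+/- 2w) after randomisation". It gives the reason for leaving the others out: "There will be no telephone call 1 for participants undergoing OIT as these participants will remain engaged with the researchers through the OIT visits". Footnote 1 to the schedule in section 7, which is attached to call 1, states the same limit by challenge result: "Only applicable to participants with a negative reaction to pHF at V2". On either wording, no pHF-reactive infant receives the call.

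The dispensing step at visit 4 (section 8.7.1.1) tells the site to prescribe enough formula to reach the next visit, "or until further product is received at home if no further OIT visits are required". The visit 5 step (section 8.7.1.2) carries the same alternative. The visit 6 step (section 8.7.1.3), at the last OIT visit, does not.

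At the call, parents answer a safety question: "They will be asked if their child has had any allergic episode where they needed to use an EpiPen, or any other adverse events". They are also asked about formula use and unplanned visits, and there is a diary prompt: "They will be reminded to fill in the diary and asked if they have enough copies of the diary".

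**The concern.** The exclusion rests on OIT visits keeping the family in touch with the site. That holds for an infant who attends visits 4, 5 and 6. It does not hold for one whose OIT ends after visit 4 or 5 and who carries on with trial formula at home, a case the dispensing steps foresee. Footnote 1 is tied to the visit 2 challenge result, so such an infant cannot be read back into call 1 once OIT is over.

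The arrangement also runs against risk. Infants who tolerated pHF at visit 2 get a scheduled safety call at about week 12. Infants who reacted to it and finish OIT early do not, although those allocated to pHF are being fed it at home. Adverse events are a listed secondary outcome (section 3.4.2), and active safety monitoring starts at randomisation (section 10.1). At stake are how soon events become known, the check on formula use, and the reminder to keep the diary.

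**Working it through.** The protocol states no figure for this gap, so there is none to reproduce. The gaps follow from the printed visit windows.

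**Inputs, in weeks from randomisation**

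| Contact | Window | Source |
|---|---|---|
| Visit 4 (pHF-reactive) or visit 3 (pHF-tolerant) | 0 | Section 3.4.1: these are the randomisation visits |
| Visit 5 | 4 to 6 | Section 8.7.1.2 |
| Visit 6 | 8 to 12 | Section 8.7.1.3 |
| Call 1 | 12 +/- 2 = 10 to 14 | Section 8.7.2 |
| Visit 7 | 24 +/- 2 = 22 to 26 | Section 8.7.3.1 |

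**Formula.** Shortest gap = earliest later contact minus latest earlier contact. Longest gap = latest later contact minus earliest earlier contact.

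**Gaps before visit 7 under the current rule**

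| Infant | Interval | Calculation | Gap (weeks) |
|---|---|---|---|
| OIT ends at visit 4 | Visit 4 to visit 7 | 22 - 0 to 26 - 0 | 22 to 26 |
| OIT ends at visit 5 | Visit 5 to visit 7 | 22 - 6 to 26 - 4 | 16 to 22 |
| Full OIT course | Visit 6 to visit 7 | 22 - 12 to 26 - 8 | 10 to 18 |
| Free feeding | Visit 3 to call 1 | 10 - 0 to 14 - 0 | 10 to 14 |
| Free feeding | Call 1 to visit 7 | 22 - 14 to 26 - 10 | 8 to 16 |

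The longest gap that the plan accepts after a full OIT course is 18 weeks. A stop at visit 4 always exceeds it, by 22 - 18 = 4 to 26 - 18 = 8 weeks. A stop at visit 5 overlaps the full-course range and exceeds 18 weeks by at most 22 - 18 = 4.

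**Is there another scheduled contact in the gap?** The adverse event row of the schedule runs visit 4, visit 5, visit 6, call 1, visit 7, call 2, visit 8, visit 9. Take out the OIT visits not attended and call 1, and visit 7 is next. The 48-hour follow-up communication belongs to the food challenges at visits 2, 3, 8 and 9, not to the OIT visits.

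**Gaps with call 1 added**

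| Infant | Last OIT visit to call 1 | Call 1 to visit 7 | Longest gap before | Longest gap after |
|---|---|---|---|---|
| OIT ends at visit 4 | 10 to 14 | 8 to 16 | 26 | 16 (26 - 16 = 10 shorter) |
| OIT ends at visit 5 | 10 - 6 = 4 to 14 - 4 = 10 | 8 to 16 | 22 | 16 (22 - 16 = 6 shorter) |

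**The case against.** The strongest reply is that the affected group may not exist. The only sign of early completion is one parenthesis, used twice. The rest of the protocol treats visits 4 to 6 as the standard course:

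- The schedule marks OIT at all three visits without condition.
- Section 9.1 describes three up-dosing hospital visits.
- Free feeding appears in the home advice only after visit 6.
- OIT infants are given stool containers for visit 7 only at visit 6.

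Who may stop early, and what contact follows, may be settled in the OIT SOP, which is not shown.

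The second reply is that the gap is cushioned. An infant who needs no more OIT has most naturally tolerated the required doses under supervision. Infants with severe anaphylaxis to the trial product stop receiving it. Parents are trained, hold autoinjectors and can reach the team. The diary is gone through at visit 7: "Collect completed pages from previous visit and review". Serious events are reportable within 24 hours of the site becoming aware.

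Much of this stands. The number affected is unknown, a stop at visit 4 is the less likely of the two cases, and diary review should recover most non-serious events. It does not remove the point. The SOP could decide who stops early, but the call 1 rule and the adverse event schedule are fixed in this protocol and exclude these infants whatever the SOP says. The 24-hour rule works only once the site knows of an event. A free-feeding infant's diary also runs from randomisation to visit 7, but with call 1 in between; after a stop at visit 4 it covers the same 22 to 26 weeks with no scheduled prompt. The stool containers cut both ways: they also suggest that early completion was allowed for at dispensing and not carried through follow-up.

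**Conclusion.** The concern holds, as a modest one. The reason given for withholding call 1 fails in a case that the protocol itself provides for, and no other scheduled contact takes its place. Such an infant goes 22 to 26 weeks (stop at visit 4) or 16 to 22 weeks (stop at visit 5) before the next scheduled contact and adverse event assessment.

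This rests on reading the dispensing wording to mean that the later OIT visits are not attended while trial formula continues. That is the natural reading, but the OIT SOP was not available to confirm it. The loss is mainly timeliness and the mid-period prompt. The primary outcome and the sample size are unaffected. The number of infants is not stated and could be zero. The change is worth making because it is cheap, concerns infants known to react to pHF, and does no harm if nobody stops early.

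**What to change.** Amend section 8.7.2 so that call 1, at 12 weeks (+/- 2) after randomisation, also goes to any OIT infant who does not go on to visit 6, in both arms.

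In the section 7 schedule, give call 1 a footnote of its own and leave footnote 1 as it is, because footnote 1 also restricts visit 3 (the cow's milk challenge) to pHF-negative infants. Suggested text for the new footnote: *Participants with a negative reaction to pHF at V2, and participants with a positive reaction who do not go on to V6.*

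The cost is a wording change, one new footnote, and one call with already defined content for each early finisher. No extra hospital visit is needed.

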8.7.3 Mid-Trial Visit 8.7.3.1 VISIT 7 (Mid Trial Visit)

Visit 7 will be conducted 24 weeks (+/- 2 weeks) from randomisation and will last up to two hours. Adherence to treatment will be checked by the research team by reviewing the diary. AEs will be reviewed and recorded **in the participant's medical notes**.

- 1. Continuation of participation will be reconfirmed.
- 2. Physical Examination, current medical history & vital signs: Weight, length, EASI Score & history of wheeze. The following will be confirmed to be normal and a statement to this effect recorded in the medical notes: general physical examination with chest auscultation, Peripheral arterial pulse, heart rate, systolic and diastolic blood pressure, respiratory rate, and oxygen saturation.
- 3. Collection of Buccal samples, blood samples and stool samples for storing: These will be collected only where **consent** has been provided, and stored locally until transferred to the central laboratory.
- 4. Unplanned visits: Any unplanned visits since the last visit and the reason for the visit, will be captured.
- 5. Collect diary from previous visit: Collect completed pages from previous visit and review. Any new AEs will be recorded in the participant's medical notes and on the AE Log and any previous AEs will be followed-up and marked as resolved if appropriate.
- 6. Provide diary and instructions for use: Give participants diary and instructions for filling in.
- 7. Provide stool sample containers for the next visit: Provide parents with containers for the collection of stool samples at home. Parents should take samples as close to visit 8 at possible, prior to the start of the challenge, and only from participants whose parents have provided **consent** for these additional samplings.
- 8. Record AEs: Any AEs occurring from this visit must be recorded in the participant's medical notes and on the AE Log (see section 10).
- 9. Record any new foods: Any new foods that have been introduced since the start of the study must be recorded in the participant's medical notes and appropriate CRF.

8.7.4 Double-blind Placebo Controlled Food Challenge (DBPCFC) 8.7.4.1 VISIT 8 (DBPCFC Day 1)

Visit 8 will be conducted 48 weeks (+/- 2 weeks) from randomisation. This visit entails Day 1 of the DBPCFC, to CM product as per the trial DBPCFC SOPs. Participants will be monitored by a delegated clinician, supported by delegated nurse(s) and will remain in the department for up to 8 hours, as appropriate. In rare cases and if they experience severe anaphylaxis, they may need to be hospitalised overnight, as per the clinical judgment of the clinician.

- 1. Confirm continuation of participation.
- 2. Physical Examination, current medical history & vital signs: Weight, length, EASI Score & history of wheeze. The following will be confirmed to be normal and a statement to this effect recorded in the medical notes: general physical examination with chest auscultation, Peripheral arterial pulse, heart rate, systolic and diastolic blood pressure, respiratory rate, and oxygen saturation.
- 3. Skin prick tests: will be conducted for cows' milk using whole, fresh milk, egg, House Dust Mite mix, cat dander, 6 grass pollen mix.
- 4. Blood sample for Antigen-specific IgE to the following Antigens: IgE levels to CM (CM-IgE), Alpha lactalbumin (ALA-IgE), beta lactoglobulin (BLG-IgE), and casein (Cas-IgE).
- 5. Collection of Buccal samples, blood samples and stool samples for storing: These will be collected only where **consent** has been provided, before the start of the challenge and stored locally until transferred to the central laboratory.
- 6. Challenge Day 1: Will be conducted as per the trial DBPCFC SOPs. Results of the DBPCFC must be recorded in the **participant's medical notes**.
- 7. Collect diary from previous visit: Collect completed diary pages from previous visit and review. Any new AEs will be recorded in the participant's medical notes and on the AE Log and any previous AEs will be followed-up and marked as resolved if appropriate.
- 8. Provide diary and instructions for use: Give participants diary and instructions for filling in.
- 9. Record AEs: Any AEs occurring from this visit must be recorded in the participant's medical notes and on the AE Log (see section 10).
- 10. Request for any unused tins to be returned at the next visit: Ask parents to return any unused tins at the next visit.
- 11. Follow up communication: A follow-up communication (phone/email) will take place within 48 hours, as per the SOPs. Any late symptoms should be recorded in the participant's medical notes, and the clinician should assess if they are possibly associated with the challenge and record this in the participant's medical notes and transcribed onto the CRFs.

